13.2. Archival of Data

The database is safeguarded against unauthorized access by established security procedures; appropriate backup copies of the database and related software files will be maintained. Databases are backed up by the database administrator in conjunction with any updates or changes to the database.

Confidential Page 22 of 28

13.3. Monitoring

This study will be monitored by representatives of the Benaroya Research Institute Clinical Research Program Administrative Office according to the U.S. CFR Title 21 Parts 50, 56, and 312 and ICH Guidelines for GCP (E6).

All study documents (patient files, signed informed consent forms, copies of CRFs, Study File Notebook, etc.) will be available for monitors and maintained for at least two years after the study is completed.

13.4. Sample Retention

Specimens collected in this trial, including genetic samples, will be deposited into the BRI Immune-Mediated Diseases Registry and Repository (IMDRR) for future research studies that have not yet been planned. Samples will be coded and stored indefinitely at the Benaroya Research Institute (BRI) in the IMDRR. We may share coded samples with colleagues at other institutions, who are doing research related to diabetes and immune-mediated disease. Identifiable personal and clinical information or "Protected Health Information" (PHI) collected from subjects is entered into the Registry and linked to a coded number. Access to this link is limited by double password to individuals directly involved in the clinical research associated with the protocol. In general, no data containing PHI will be provided to recipient investigators from the IMDRR unless a Data Use Agreement (DUA) has been established and disclosure is approved by the IRB. Samples collected for pharmacokinetic analysis will be shipped frozen to the Janssen Research and Development Biologics Clinical Pharmacology laboratory.

14.ADMINISTRATIVE, ETHICAL, REGULATORY CONSIDERATIONS

14.1.Benefit of Participation

This study will not provide any direct benefit to the study subjects aside from the general benefits of closer health monitoring associated with participating in a clinical study. Future patients may benefit from these studies by virtue of knowledge gained about the pathophysiology of blocking cell activation by IL-6.

14.2. Risks of Participation and Mitigation of Risks

The possible discomforts, side effects, and risks related to Siltuximab treatment are not all known. Most side effects are not serious. Some may be serious and may require treatment or additional testing. Side effects seen on research studies can result from a patient's disease, the experimental drug, other drugs, other diseases, or a combination of these. These side effects may or may not have been due to Siltuximab.

The risk of administering Siltuximab to T1D patients is considered low because (a) subjects will only

Confidential Page 23 of 28

receive a single infusion of the drug, and (b) all subjects enrolled will have T1D, but no other medical conditions that increase their risk of adverse effects. Most of the reported adverse effects were associated with long-term administration of the drug. In patients receiving a single dose of drug, the primary risk is of a hypersensitivity reactions to the product. Approximately 750 individuals have been treated with Siltuximab. Of these, one patient experienced an anaphylactic reaction. Data from 249 patients treated with Siltuximab monotherapy form the basis of the safety evaluation of infusion-related reactions. Infusion related reactions were reported in 4.8% of these patients. Symptoms of infusion-related reactions consist of back pain, chest pain or discomfort, nausea and vomiting, erythema, and palpitations.

T1D patients enrolled in the EMU-002 study will be screened for previous reactions, including anaphylaxis to human, humanized or murine monoclonal antibodies. In addition, all infusions will occur on the Clinical Research Center where subjects are closely monitored by experienced personnel equipped with resuscitation medications to address any such reactions including anaphylaxis to study drug administration.

Other adverse effects reported in patients treated chronically with Siltuximab included upper respiratory infections, renal injury, lipidemia, and low platelet and neutrophil counts. These potential effects will be mitigated by excluding subjects with those pre-existing conditions from participation in the study.

Finally, the effect of Siltuximab on human sperm, pregnant women, breastfeeding women, unborn babies, or nursing infants has not been studied. For this reason female subjects enrolled in this study must have a pregnancy test to confirm that they are not pregnant. A full summary of reported adverse events is provided in the Prescribing Information.

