7. SUBJECT SELECTION

7.1. Study Population

Study subjects will include males and females 18-45 years of age with a diagnosis of Type 1 diabetes within 10 years of enrollment.

7.2.Inclusion criteria

Each potential subject must satisfy all of the following criteria before enrollment:

1. Positive for at least one diabetes-related autoantibody any time since diagnosis, including by not limited to:

Confidential Page 9 of 28

- Glutamate decarboxylase (GAD-65) Insulin, if obtained within 10 days of the onset of exogenous insulin therapy
- IA-2
- ZnT8
- 2. Peak stimulated C-peptide level ≥ 0.1 pmol/mL following a mixed meal tolerance test (MMTT) conducted within 60 days of enrollment
- Females of child-bearing potential must be willing to use effective birth control and refrain from donating eggs for the purposes of assisted reproduction for duration of study.
- 4. A woman of childbearing potential must have a negative serum (β -human chorionic gonadotropin [β -hCG]) or urine pregnancy test at screening and prior to dosing.
- 5. During the study, and for 3 months after receiving the study agent, a woman must agree to not donate eggs (ova, oocytes) for the purposes of assisted reproduction.
- 6. Willing and able to give informed consent for participation.

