11.2.5. Special Reporting Situations

Adverse events of interest for a Janssen medicinal product that require expedited reporting and/or safety valuation include, but are not limited to:

- Drug exposure during pregnancy (maternal and paternal);
- Overdose of a Janssen medicinal product;
- Exposure to a Janssen medicinal product from breastfeeding;
- Suspected abuse/misuse of a Janssen medicinal product;
- Inadvertent or accidental exposure to a Janssen medicinal product;
- Medication error involving a Janssen medicinal product (with or without patient exposure to the Janssen medicinal product, e.g., name confusion);
- Suspected transmission of any infectious agent via administration of a medicinal product;
- Any failure of expected pharmacological action (i.e., lack of effect) of a Janssen medicinal product
- Unexpected therapeutic or clinical benefit from use of a Janssen medicinal product

These safety events may not meet the definition of an adverse event; however, from a Janssen Research & Development perspective, they are treated in the same manner as adverse events.

Confidential Page 17 of 28

Any special situation that meets the criteria of a serious adverse event should be recorded on a Serious Adverse Event Report Form and be reported to the COMPANY within 24 hours of becoming aware of the event.

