11.4. Procedures for Reporting to Janssen Research & Development

The Sponsor Investigator will provide safety information to Janssen Research & Development on adverse events, special situations including pregnancies and product quality complaints as defined within this section.

11.4.1.Serious Adverse Events

Serious adverse events that are unexpected and possibly or probably drug related as defined in Section 11.2.4 will be reported to Janssen Research & Development using FDA Form MedWatch 3500A within 24 hours of becoming aware of the event. Serious adverse events, with the exception of pregnancies, will be reported for 30 days after the last dose of study drug.

All follow-up information for serious adverse events that are not resolved at the end of the study or by the time of patient withdrawal must be reported directly by the Sponsor Investigator, within 24 hours of becoming aware, to Janssen Research & Development.

All available clinical information relevant to the evaluation of a related SAE or special situation is required. The Sponsor Investigator is responsible for ensuring that these cases are complete and if not are promptly followed-up. A safety report is not considered complete until all clinical details needed to interpret the case are received. Reporting of follow-up information should follow the same time line as initial reports and contain the elements summarized in section 11.2.5.

11.4.2.. Adverse Events of Special Interest

Adverse events of special interest (≥ Grade 2), as defined in Section 11.2.2, will be reported to Janssen Research & Development on a quarterly basis unless they are serious adverse events. Serious adverse events will be reported within 24 hours of learning of the event.

11.4.3.Pregnancies

Any subject who becomes pregnant during the study must be promptly withdrawn from the study and discontinue further participation.

Pregnancies in female participants or partners of male participants will be reported to Janssen Research and Development within 24 hours of learning of the event using the FDA MedWatch 3500 A form. Follow-up information regarding the outcome of the pregnancy and any postnatal sequelae in the infant will be required. Depending on local legislation this may require prior consent of the partner of the male participant.

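### Section 14.2 names human sperm as unstudied and men are eligible, but the plan's bar on gamete donation (7.2 items 3 and 5) applies to eggs only

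*Combined protocol and SAP*

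**What the plan says.** All references are to the combined protocol and SAP.

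- **Section 7.1** makes both sexes eligible: "Study subjects will include males and females 18-45 years of age".
- **Section 14.2** gives the state of knowledge: "the effect of Siltuximab on human sperm, pregnant women, breastfeeding women, unborn babies, or nursing infants has not been studied". The measure it draws from this is: "For this reason female subjects enrolled in this study must have a pregnancy test to confirm that they are not pregnant".
- **Section 7.2, item 3** (its numeral is lost in the extracted text, but it stands between items 2 and 4) requires females of child-bearing potential to be willing to "use effective birth control and refrain from donating eggs for the purposes of assisted reproduction for duration of study".
- **Section 7.2, item 5** applies during the study and also sets a period counted from dosing: "for 3 months after receiving the study agent, a woman must agree to not donate eggs (ova, oocytes) for the purposes of assisted reproduction".
- **Section 11.2.5** lists paternal as well as maternal exposure during pregnancy as a special reporting situation.
- **Section 11.4.3** covers partners: "Pregnancies in female participants or partners of male participants will be reported". The report is due to the company within 24 hours, with follow-up on the outcome of the pregnancy and on the infant.

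**The concern.** Section 14.2 sets out risks and how they are mitigated. It names five unstudied matters and answers with a test that cannot bear on one of them, sperm. That alone would be a loose sentence in a summary section. It matters more because 7.2 already contains a precaution of the relevant kind, a bar on gamete donation, and applies it to one sex only.

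At stake is the protection of people outside the trial, namely the recipient of donated sperm and any resulting child, and the plan's consistency with its own precautionary standard. As the supplied text stands, a man could donate sperm the day after infusion without breaching the protocol, while a woman could not donate eggs for 3 months.

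**Working it through.** No figure in the plan bears on this point, so the check is a side-by-side reading, a count and one comparison of periods.

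**1. Which reproductive items could have a male counterpart?**

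| Provision | Applies to | Male counterpart possible? |
|---|---|---|
| 7.2 item 3, birth control | women | yes |
| 7.2 item 3, no egg donation | women | yes (sperm donation) |
| 7.2 item 4, pregnancy test | women | no |
| 7.2 item 5, no egg donation | women | yes (sperm donation) |
| 7.3 item 10, pregnant or lactating | women | no |
| 11.2.5, exposure in pregnancy | both | already covers men, by report |
| 11.4.3, pregnancy | both | already covers men's partners, by report |

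Two items (3 and 5) bar egg donation. None bars sperm donation. Items 3 and 5 overlap during the study, so this is one precaution stated twice, not two separate ones.

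**2. Can the female-only rule be explained by the route of exposure?** The two parts of item 3 need separate answers.

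- *Birth control.* A dosed woman who conceives carries the fetus during her own drug exposure; a dosed man does not. That difference can justify a female-only rule.
- *Egg donation.* A donated egg leaves the donor, and the pregnancy is carried by someone else. The fetus is then not exposed through the donor's circulation, so the concern left is the gamete itself. The same reasoning applies to donated sperm. Item 5 also counts its 3 months from receipt of the agent, which ties the bar to drug exposure.

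**3. Does the general low-risk argument explain it?** Section 14.2 calls the risk low partly because each subject receives a single infusion. Women also receive a single infusion and still have the donation bar, so this argument does not separate the sexes.

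**4. Over what period is there a difference?** The last visit is at Day 84 ± 7, so 84 − 7 = Day 77 to 84 + 7 = Day 91. Three calendar months from dosing is 89 to 92 days. The egg-donation bar in item 5 therefore runs from dosing to about Day 89 to 92. For sperm donation the corresponding period is 0 days.

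**5. How many subjects?** The accrual objective is 10 and the supplied text sets no sex quota, so anywhere from 0 to 10 of those 10 may be men.

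**The case against.** The strongest case on the other side has four parts.

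- **Unseen text.** Advice to men would naturally sit in the consent form, whose pages were removed before review, or in the prescribing information, which is Attachment 2 but survives only as a link. Section 14.3 has the IRB approve the protocol and consent documents. This stands as a limit: it cannot be said that men receive no advice. It does not supply a male item in 7.2.
- **Section 14.2 is a summary.** Four of its five unstudied matters concern pregnancy or breastfeeding, for which a pregnancy test is a sensible answer. The section also leaves out the plan's own birth-control and egg-donation items. This too stands: the silence of 14.2 is weak evidence on its own. The point rests on 7.2, where the donation bar exists for one sex only.
- **Different rules by sex can be deliberate.** For birth control this is right. A reader might infer that the plan must also require male contraception. The documents do not support that: they show no paternal hazard, and the difference in fetal exposure is a good enough reason for a female-only rule. The reason does not carry over to donated gametes.
- **The plan did consider men.** It did, in 11.2.5 and 11.4.3, so a reader who infers that male exposure was ignored would be wrong. But both provisions act after an exposure or pregnancy has occurred. Neither aims to prevent one, and donation to an unknown recipient is the case in which a partner-pregnancy report is least likely to reach the site.

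**Conclusion.** The point holds in a narrow form. The plan bars donation of eggs during the study and for 3 months after dosing, and does not bar donation of sperm, although 14.2 names sperm as unstudied and men are eligible. The supplied text gives no reason for the difference.

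The point is minor. It affects no endpoint, analysis or sample size, concerns at most the men among 10 planned subjects, and covers about three months each. It rests on two assumptions: that the egg-donation bar is a precaution about the gamete (the plan states no reason, but the period counted from dosing points that way), and that the consent form and prescribing information do not already bar sperm donation. If they do, what remains is a missing item in 7.2 and a missing cross-reference in 14.2. Nothing here shows that siltuximab harms sperm or offspring; the documents say only that this has not been studied.

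**What to change.** Add one inclusion item to 7.2, worded as item 5 is but with a man in place of a woman and sperm in place of eggs, so that the period is the same: throughout the study and up to 3 months from the infusion. Cite it in 14.2 beside the pregnancy test, and add matching consent wording if it is not already there. Leave male birth control to the sponsor's judgement. If the sponsor considers a sperm-donation bar unnecessary after a single dose, a sentence in 14.2 giving the reason would also remove the inconsistency.

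Cost: one eligibility item, one cross-reference and possibly one line of consent text, with no added visit, test or sample. The downside is a very small restriction on male participants.

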14.3. Statement of Compliance

This study will be conducted in compliance with the protocol and consistent with current Good Clinical Practices (GCP), adopting the principles of the Declaration of Helsinki, and all applicable regulatory requirements (ICH E6, 45CFR46, and FDA 21CFR sections 11, 50, 56, 312).

Prior to study initiation, the protocol and the informed consent documents will be reviewed and approved by the Benaroya Research Institute at Virginia Mason Institutional Review Board (IRB). Any amendments to the protocol or consent materials will also be approved by the IRB.

14.4.Informed Consent

The process of assuring that individuals (and parent/guardian if less than 18 years of age) are making an informed decision about participating in this study includes both verbal and written communication. All participants must read, sign, and date a consent form before participating in the study, taking the study drug, and/or undergoing any study-specific procedures.

The informed consent form must be updated or revised whenever important new safety

information is available, whenever the protocol is amended, and/or whenever any new information becomes available that may affect participation in the trial.

A copy of the informed consent will be given to a prospective participant for review. The attending health care provider will review the consent and answer questions.

14.5. Withdrawal of Subjects from the Study

A subject may be withdrawn from the study at any time if the subject or the Investigator feels that it is not in the subject's best interest to continue. All subjects are free to withdraw from participation at any time, for any reason, specified or unspecified, and without prejudice. Reasonable attempts will be made by the Sponsor Investigator to provide a reason for subject withdrawals. The reason for the subject's withdrawal from the study will be specified in the subject's source documents.

Individuals without evaluable mechanistic data may be replaced.

Attachment 1. Schedule of Procedures

Attachment 2. SYLVANT Prescribing Information and Dosing Instructions (http://www.sylvant.com/shared/product/sylvant/sylvant-prescribing-information.pdf)

ATTACHMENT 1. Schedule of Events

Table 1. Study Procedures						
Visit Number	1	2	3	4	5	6
Time Point (Day)	-14	0	1.	14 ^b	28 ^b	84 ^b
Visit Window (Day)	+/- 7	-	-	+/- 3	+/- 3	+/- 7
General Assessments	Х	Х	Х	Х	х	Х
Vital Signs	Х	Х	Х			
Islet Autoantibodies	Х					
MMTT ^a	Х					
HbA1c	Х					
HIV, HBV, HCV serology	Х					
QuantiFERON TB test	Х					
EBV, CMV Serology	Х					
EBV, CMV viral load	Х					
Urine Pregnancy Test	Х	Х				
Comprehensive chemistry panel	Х	Х	Х	Х	Х	Х
Lipid Panel	Х	Х	Х	Х	Х	Х
C-reactive Protein	Х	Х	Х	Х	Х	Х
Direct bilirubin	Х	Х	Х	х	Х	Х
Erythrocyte sedimentation rate	Х	Х	Х	Х	Х	Х
CBC	Х	Х	Х	х	Х	Х
HLA Typing and SNP Analysis	Х					
Mechanistic Assays	Х	Х	Х	Х	Х	Х
Pharmacokinetic Samples	Х	Х	Х	Х	Х	Х

^a if not performed within 60 days of study screening visit

^b blood draw Visits 4-6 may be conducted remotely
